assessing the mechanism of side-branch compromise following intervention in bifurcation lesions. The recent development of OCT with online 3D reconstruction allows the operator to obtain a 3D visualization of the lesion and may provide a unique tool for guidance during complex bifurcation PCI and potentially improve stenting results. 3D OCT has been used to visualize jailed side branches after implantation of bioresorbable scaffolds in the main branch and develop a new classification system based on the number of SB compartments. In addition, its potential clinical application in guiding the rewiring of the distal compartment of the SB ostium (jailed with stent struts after MB stenting) to minimize the risk of floating struts was demonstrated. It is important to note that while OCT, 3D-OCT, and 3D-QCA (such as that used in the ORBID trial) are imaging modalities that can be used to answer important research questions, their wide-spread adoption in daily clinical practice has been very limited. Intravascular ultrasound (IVUS) is used more frequently as part of a PCI guidance strategy in daily clinical practice.

Fractional flow reserve (FFR) is a pressure-derived, lesion specific index used to determine the functional significance of coronary artery stenosis. Several studies showed that FFR is a safe and feasible method to assess the significance of an ostial SB stenosis after provisional stenting. Quantitative coronary angiography (QCA) has been shown to be unreliable in assessing the functional significance of SB after stent implantation in MV (the area under the curve 0.64, 41.5% sensitivity and 83.1% specificity) suggesting that treatment decisions for jailed SB should not be based on angiographic findings alone. A recent report demonstrated a better ability of post-PCI 3D-OCT to predict the functional significance for SB ostial lesions caused by a jailed SB outcome.

A previous study (ORBID) of 30 patients was done at Mount Sinai Hospital and aimed to identify the predictors of side branch (SB) ostial stenosis developed after provisional stenting of the main vessel (MV) using Optical Coherence Tomography (OCT). The study Showed that High lipid content of the MV lesion and a contralateral location of lipid in the bifurcation area may contribute to SBOS after provisional stenting.

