 Mount Sinai	Protocol Title:	Optical Coherence Tomography Predictors of Functionally Significant Side Branch Compromise after Provisional Main Vessel Stenting In Bifurcation Lesions Assessed by Fractional Flow Reserve (ORBID – FFR)
	Principal Investigator Name/Contact Info:	[name]./ [name]/ [name]
	Primary Contact Name/Contact Info	[name] /[name] / [name] [name] /[name] [name]
	Date Revised:	January 19, 2017
	Study Number:	HSM# 16-00041/ GCO#1: 16-0204(0001)

Data analysis and Statistical methods:

T-test will be used. OCT off-line image analysis. For the accurate characterization of bifurcation lesions, OCT images will be analyzed systematically at 1 mm intervals according to previously validated criteria for plaque characterization using the St. Jude Medical Offline Review Workstation as we described previously. In addition, three-dimensional OCT software (QAngio OCT, Medis) will be used to obtain the information for the side branch ostium from a single main branch pullback as described recently in a validation of cut plane analysis (Figure 2). We will also perform three-dimensional quantitative coronary angiography (3D-QCA) using QAngio XA 3D software (Medis) to obtain the measurements of bifurcation angles, stenosis, and references. This software is dedicated to bifurcation lesions and has shown to provide highly accurate assessment of lesion dimensions and geometry based on 3D reconstruction of bifurcation lesions. Offline analysis of side branch for impingement of the ostium of SB leading to acute loss in SB diameter, area, carina shift and plaque shift will be performed and 3D-OCT parameters will be correlated with SB FFR measurements.

 Mount Sinai	Protocol Title:	Optical Coherence Tomography Predictors of Functionally Significant Side Branch Compromise after Provisional Main Vessel Stenting In Bifurcation Lesions Assessed by Fractional Flow Reserve (ORBID – FFR)
	Principal Investigator Name/Contact Info:	[name]./ [name]/ [contact]
	Primary Contact Name/Contact Info	[name] /[name] / [contact] [name] /[name] [contact]
	Date Revised:	January 19, 2017
	Study Number:	HSM# 16-00041/ GCO#1: 16-0204(0001)

[figure not shown]

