Figure 2. 3D quantitative coronary angiography (QCA) and cut-plane analysis of side branch ostium from the main branch OCT pullback for bifurcation PCI before (top row) and after (bottom row) stenting.

We assumed FFR (+) prevalence of either 20% or 25% based on previous studies. We also assumed that there would be a roughly equal proportion of patients with high and lipid levels.

Based on these assumptions, we will need at least 75 patients per EACH high lipid and low lipid groups to detect an odds ratio (OR) of 2.8.

Protocol Title:	Optical Coherence Tomography Predictors of Functionally Significant Side Branch Compromise after Provisional Main Vessel Stenting In Bifurcation Lesions Assessed by Fractional Flow Reserve (ORBID – FFR)
Principal Investigator Name/Contact Info:	[name]./ [name]/ [contact]
Primary Contact Name/Contact Info	[name] /[name] / [contact] [name] /[name] [contact]
Date Revised:	January 19, 2017
Study Number:	HSM# 16-00041/ GCO#1: 16-0204(0001)

The table below is showing the detectable OR we might have under different assumptions of the patient population assuming an equal proportion of high/low lipid level groups.

Prevalence of + FFR	Patients per group	Detectable OR with 80% power
0.2	50	3.7
0.2	75	2.9
0.2	100	2.5
0.25	50	3.5
0.25	75	2.8
0.25	100	2.4

a) Recruitment Methods

We will recruit patients referred to the interventional cardiologists involved on this study based on their medical history who require a PCI of the main vessel with drug eluting stent implantation for the treatment of stable CAD where impact on the side branch can be access. Patients will be undergoing a PCI using an angiography and OCT-guided strategy. Patients will be approached in the ambulatory unit before their procedure to obtain consent and review and confirm the inclusion and exclusion criteria of the protocol.

The PI and the research team will identify potential subjects based on their medical history. Potential patients will be approached in the ambulatory unit before their procedure to obtain consent and check the inclusion/exclusion criteria.

In all cases, the Principal Investigator, Sub-Investigator or member of the Research Team will discuss the research trial and informed consent document in full detail following Good Clinical Practices and HIPAA Laws. During the informed consent process, all of the potential subject's questions will be answered. Subjects will be given a copy of the signed

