Date Revised:	January 19, 2017
Study Number:	HSM# 16-00041/ GCO#1: 16-0204(0001)

General exclusion criteria: Patient will not be enrolled in the study if ANY of the following criteria are present in the patient.

- Patients with ostial left main artery lesions or ostial right coronary artery lesions
- Female patients with child bearing potential not taking adequate contraceptives or currently breastfeeding
- Known allergy to acetylsalicylic acid or clopidogrel.
- Planned surgery within 12 months.
- History of bleeding diathesis
- Major surgery within 15 days
- Life expectancy < 12 months.
- Patients with kidney dysfunction (CrCl<30)

c) Number of Subjects

One hundred and fifty (150) consecutive patients with lesions requiring PCI of main vessel with drug eluting stent implantation for the treatment of stable CAD will be included in the study.

d) Study Timelines

This is a randomized study with one visit and no clinical follow-ups.

e) Study Endpoints

The primary endpoint is SB compromise defined as SB DS \geq 70%, or dissection or TIMI < 3.

The secondary endpoints

- SB FFR after main vessel stenting and its correlation with OCT imaging parameters before PCI
- OCT predictors of SB TIMI flow reduction after main vessel PCI
- Off-line analysis of SB stenosis by 3D-OCT and its correlation with FFR; correlation between 3D-QCA measurements, 3D-OCT, and FFR data.

Protocol Title:	Optical Coherence Tomography Predictors of Functionally Significant Side Branch Compromise after Provisional Main Vessel Stenting In Bifurcation Lesions Assessed by Fractional Flow Reserve (ORBID – FFR)
Principal Investigator Name/Contact Info:	[name]./ [name]/ [contact]
Primary Contact Name/Contact Info	[name] /[name] / [contact] [name] /[name] [contact]
Date Revised:	January 19, 2017
Study Number:	HSM# 16-00041/ GCO#1: 16-0204(0001)

- Association between calcification assessment by angiography and OCT imaging.
- FFR Device Success (ability to successfully deliver FFR wire to desired SB distal segment [n/150]).
- FFR Wire Workhorse Capability (proportion of patients [n/150] in which FFR wire able to serve as rail to deliver additional interventional devices to target SB lesion).

f) Procedures Involved in the Human Research

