Stable CAD patients with bifurcation lesions in whom provisional stenting strategy is planned, who have moderate or severe calcification in the main vessel lesion identified by angiography, SB stenosis 30-70% and SB reference diameter > 2mm will be enrolled in the study.

Moderate calcification will be defined as radiopaque density observed only during the cardiac cycle and typically involving only one side of the vascular wall, and severe calcification will be defined as radiopaque density noted without cardiac motion prior to contrast injection and involving both sides of the arterial wall. After completion of diagnostic angiogram and confirmation of subject eligibility, subjects will be randomly assigned to Rotational atherectomy (RA or Cutting Balloon Angioplasty (CBA)/PTCA group in a 1:1 fashion.

Patients in both groups will undergo PCI with stent implantation according to current standards of care. Lesion preparation including lesion pre-dilation, scoring or sculpting balloon angioplasty, and use of atherectomy and protection devices will be performed at the operator's discretion, followed by MV stenting. The operator will also decide in both groups about the length and size of the implanted stent. Procedural optimization, such as post-dilation or additional stent implantation will be performed based only on the angiographic findings, according to the discretion of the operator.

Protocol Title:	Optical Coherence Tomography Predictors of Functionally Significant Side Branch Compromise after Provisional Main Vessel Stenting In Bifurcation Lesions Assessed by Fractional Flow Reserve (ORBID – FFR)
Principal Investigator Name/Contact Info:	[name]./ [name]/ [contact]
Primary Contact Name/Contact Info	[name] /[name] / [contact] [name] /[name] [contact]
Date Revised:	January 19, 2017
Study Number:	HSM# 16-00041/ GCO#1: 16-0204(0001)

Optical coherence tomography (OCT) is an established medical imaging technique that uses light to capture micrometer-resolution, three-dimensional images from within optical scattering media will be performed to analyze plaque morphology, the extent and location of calcification, side branch size, angle, and ostial involvement.

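### The search for OCT predictors names about 8 to 15 candidates but no confirmatory one, leaving roughly a 19–46% chance of at least one false predictor across 8 to 12 null parameters

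*Combined protocol and SAP*

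**What the plan says.** The Objectives section makes OCT predictors of FFR ≤ 0.8 part of the research question, and the title says the same. Under Study Endpoints, the correlation of side-branch FFR with pre-PCI OCT parameters and the OCT predictors of TIMI flow reduction are secondary. The primary endpoint is side-branch compromise.

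The candidates are spread over three sections:

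- Procedures Involved in the Human Research lists plaque morphology and "the extent and location of calcification, side branch size, angle, and ostial involvement".
- Data analysis and Statistical methods adds bifurcation angle, stenosis and reference size from 3D-QCA, and an offline analysis of "acute loss in SB diameter, area, carina shift and plaque shift will be performed and 3D-OCT parameters will be correlated with SB FFR measurements".
- Background reports that the earlier 30-patient study pointed to lipid content and contralateral lipid location.

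The test specification is one sentence: "T-test will be used". No outcome, grouping, significance level, model or multiplicity rule is attached to it.

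The sample size rests on a single predictor: "we will need at least 75 patients per EACH high lipid and low lipid groups to detect an odds ratio (OR) of 2.8". The prevalence behind it is also given: "We assumed FFR (+) prevalence of either 20% or 25% based on previous studies". Lipid then appears in neither the analysis text nor the endpoint list.

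**The concern.** When many measurements are screened and no rule says which result counts, any parameter that crosses p < 0.05 can be reported as a predictor. The error rate that matters is then the chance that at least one of them does so by luck, and that is well above 5%.

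The plan already holds what is needed to avoid this. One predictor had prior evidence and was used to justify the sample size, but the analysis text does not give it that role. A lipid result would stand level with every other parameter, and a negative lipid result could be displaced by whichever measurement happened to reach significance.

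The stated test also does not match the sizing. The sample size is expressed as an odds ratio for a binary outcome, and a t-test does not estimate an odds ratio.

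**Working it through.** **1. The plan's own figure.** Inputs from the sample-size paragraph and table: FFR-positive prevalence 25%, odds ratio 2.8, 75 per group, power 80% (column heading "Detectable OR with 80% power"). Alpha is not stated; take two-sided 0.05. Read the prevalence as the rate in the low-lipid group.

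- High-lipid rate: p₂ = 2.8 × 0.25 / (1 − 0.25 + 2.8 × 0.25) = 0.70 / 1.45 = 0.483. Difference d = 0.233, mean rate 0.366.
- n = [1.960·√(2 × 0.366 × 0.634) + 0.842·√(0.25 × 0.75 + 0.483 × 0.517)]² / d² = 66.1, so 67 per group.
- With continuity correction: (n/4)·[1 + √(1 + 4/(n·d))]² = 74.4, so **75 per group, as stated**.

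The same method gives detectable odds ratios of 3.72, 2.94, 2.55, 3.52, 2.79 and 2.43 for the six cells, against the table's 3.7, 2.9, 2.5, 3.5, 2.8 and 2.4. The sizing is therefore a two-sided 5% comparison of two proportions for one predictor. That supports 5% as the working alpha, though it remains an assumption for the predictor search.

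**2. Number of candidates.**

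- Pre-PCI OCT: plaque morphology, calcium extent, calcium location, side-branch size, angle, ostial involvement = 6. Adding lipid content and lipid location gives **8**.
- 3D-QCA: angle, stenosis, reference size = 3. Offline side-branch measures: diameter loss, area loss, carina shift, plaque shift = 4. The total is 8 + 3 + 4 = **15**.
- Some overlap (angle appears twice; diameter and area loss describe the same ostium), so about **12** is a reasonable middle count.

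**3. Chance of at least one false predictor.** Assume all nulls are true, each parameter is tested at 0.05, and there is one outcome. If the tests are independent, the chance is 1 − 0.95ᵏ:

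- k = 8: 1 − 0.95⁸ = 33.7%
- k = 12: 1 − 0.95¹² = 46.0%
- k = 15: 1 − 0.95¹⁵ = 53.7%

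For equally correlated normal test statistics:

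| Pairwise correlation | 8 parameters | 12 parameters | 15 parameters |
|---|---|---|---|
| 0 | 34% | 46% | 54% |
| 0.3 | 30% | 40% | 46% |
| 0.5 | 25% | 32% | 36% |
| 0.7 | 19% | 23% | 26% |

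These rates do not depend on the number of patients. Counting TIMI flow reduction as a second outcome would raise them.

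**4. Cost of a blanket correction.** Bonferroni over 12 tests each at 0.05/12 = 0.0042. For the lipid comparison (25% versus 48.3%, 75 per group, no continuity correction), power falls from 84.8% to 53.8%. Restoring 80% would need about 117 per group. Naming one confirmatory predictor avoids that loss.

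**The case against.** The strongest reply is that these are secondary analyses, that the plan is silent on adjustment rather than committed to an unadjusted procedure, and that unadjusted secondary predictor work is common when labelled exploratory. Several analyses are described as correlations, so it is not accurate to say that the plan prescribes an unadjusted t-test for each parameter. The all-null case is also extreme, since Background cites earlier evidence for lipid and for post-PCI 3D-OCT against FFR.

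Most of this stands, and it limits how strongly the point can be put. It does not remove the point: a p-value per correlation multiplies in the same way as a p-value per t-test, the plan does not label the search exploratory, and it gives the sized predictor no role in the analysis.

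Two stronger readings are tempting, and the documents support neither.

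- A reader might take 40–46% as the least the error could be. That range needs 12 parameters with pairwise correlation no higher than about 0.3. The FFR endpoint that concerns pre-PCI OCT covers about 8 parameters, and measures of the same ostium may be more strongly correlated.
- A reader might infer that a score built from noise would match the QCA figures in Background ("the area under the curve 0.64, 41.5% sensitivity and 83.1% specificity"). No score, study AUC or comparison with that value is planned. In simulations of 12 noise parameters in 150 patients, a score built only from parameters with p < 0.05 existed and reached 0.64 in about 7–24% of runs (11–26% in a separate logistic version), so this is not the expected result.

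**Conclusion.** The point holds as a gap in specification with a measurable consequence. About 8 to 15 candidates are named and the test is given in one sentence. The predictor behind "One hundred and fifty (150) consecutive patients" is not designated for testing. The chance of at least one false predictor is about 23–46% for 12 parameters and 19–34% for 8, against a nominal 5%. Even the low end is nearly four times nominal.

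These figures assume two-sided 0.05 per parameter, all nulls true, one outcome, and pairwise correlation between 0.7 and 0. The documents fix neither alpha, the count nor the correlation. The primary endpoint, side-branch compromise, is not affected. This is a cheap improvement that changes what the trial may claim about predictors.

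**What to change.** In Data analysis and Statistical methods, and in the sample-size paragraph that follows it:

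1. Name main-vessel lipid on the pre-stent OCT pullback, high versus low with the cut-off fixed in advance, as the single confirmatory predictor of side-branch FFR ≤ 0.8 at two-sided 5%. State that it is the one confirmatory test among the secondary predictor analyses.
2. Analyse it as an odds ratio with a 95% confidence interval, by logistic regression or a two-proportion test, in place of the t-test. This matches the sizing.
3. List the remaining parameters, label them exploratory, and report them with confidence intervals. False-discovery-rate adjusted p-values are optional.
4. Only if a multi-parameter score is built, report a bootstrap optimism-corrected AUC with the selection step repeated in every resample.

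The cost is a few lines of text and code, with no change to recruitment or procedures. The downside is that fewer parameters can be called predictors.

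### The detectable-OR table uses the 20%/25% FFR-positive prevalence as the low-lipid group's rate; taken as the population prevalence, 75 per group gives less than 80% power for an OR of 2.8

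*Combined protocol and SAP*

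**What the plan says.** The sample-size paragraph is at the end of Data analysis and Statistical methods (section 5, Study Design). It gives two assumptions: "We assumed FFR (+) prevalence of either 20% or 25% based on previous studies", and "We also assumed that there would be a roughly equal proportion of patients with high and lipid levels" (the word for the second group is evidently missing). It concludes that "we will need at least 75 patients per EACH high lipid and low lipid groups to detect an odds ratio (OR) of 2.8".

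A six-row table follows, introduced as covering "different assumptions of the patient population assuming an equal proportion of high/low lipid level groups". Its columns are the prevalence of positive FFR, the patients per group, and "Detectable OR with 80% power". For 50, 75 and 100 per group it prints 3.7, 2.9 and 2.5 at prevalence 0.20, and 3.5, 2.8 and 2.4 at 0.25.

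Number of Subjects sets enrolment at 150, which is twice 75. No alpha, sidedness or test is given for the OR comparison. The only test named in the section is in "T-test will be used".

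**The concern.** A prevalence taken from previous studies and offered as an assumption about the patient population is naturally read as the rate across all patients. With equal lipid groups, that is the average of the two group rates. A detectable OR also depends on how the prevalence is split between groups. If the same 20% or 25% is used as the rate in the lower-risk group, the other group sits well above it. The calculation then assumes more events than the stated prevalence supplies, and the detectable OR looks smaller than it should.

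This is the only power statement in the protocol and the only stated basis for 150 patients. If it is optimistic, a lipid comparison without a significant difference could be taken as 80%-power evidence against an OR of 2.8 when the study did not have that power.

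There is also a smaller mismatch. The text gives OR 2.8 for a prevalence of either 20% or 25%, but at 75 per group the table gives 2.8 only at 25%, and 2.9 at 20%.

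**Working it through.** **Inputs.** From the protocol: prevalence 0.20 or 0.25, equal groups, 75 per group, 80% power, OR 2.8. Assumed, because not stated: two-sided alpha 0.05 and a two-proportion test.

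**Formulas.** With low- and high-lipid rates pL and pH, d = pH − pL and mean p̄:

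- pH = OR·pL / (1 − pL + OR·pL)
- n = [1.960·√(2p̄(1−p̄)) + 0.8416·√(pL(1−pL) + pH(1−pH))]² / d²
- continuity-corrected n = (n/4)·[1 + √(1 + 4/(n·d))]²
- power = Φ{[d·√n − 1.960·√(2p̄(1−p̄))] / √(pL(1−pL) + pH(1−pH))}, with d replaced by d − 1/n when corrected

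**Step 1: reproduce the plan's figure.** Take 25% as the low-lipid rate and OR 2.8.

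- pH = 0.70/1.45 = 0.483, d = 0.233, p̄ = 0.366.
- n = (1.3355 + 0.5565)² / 0.2328² = 66.1.
- Corrected n = 74.4, which rounds up to 75, the plan's number.

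Solving the corrected formula for the OR in each row:

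| Prevalence | n per group | Printed OR | Low-lipid rate, corrected | Overall prevalence, uncorrected | Overall prevalence, corrected |
|---|---|---|---|---|---|
| 0.20 | 50 | 3.7 | 3.72 | 4.60 | 5.46 |
| 0.20 | 75 | 2.9 | 2.94 | 3.34 | 3.70 |
| 0.20 | 100 | 2.5 | 2.55 | 2.80 | 3.01 |
| 0.25 | 50 | 3.5 | 3.52 | 3.92 | 4.47 |
| 0.25 | 75 | 2.8 | 2.79 | 2.99 | 3.24 |
| 0.25 | 100 | 2.4 | 2.43 | 2.56 | 2.71 |

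The low-lipid column agrees with print within about 0.05 throughout. Its one rounding miss is 2.55 printed as 2.5. Fisher's exact test on the same reading also comes close, with 78% to 81% power at the printed ORs. No method tried under the overall-prevalence reading reproduces all six rows.

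**Step 2: what the table then implies.** At 75 per group the high-lipid rate is 42.0% (20%, OR 2.9) or 48.3% (25%, OR 2.8). Overall prevalence is (20 + 42.0)/2 = 31.0% or (25 + 48.3)/2 = 36.6%.

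**Step 3: hold overall prevalence at the stated value.** Require (pL + pH)/2 = 0.25 or 0.20, with OR 2.8 and 75 per group.

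- At 25%: pL = 0.157, pH = 0.343, d = 0.1858. Uncorrected power = Φ[(1.6091 − 1.2002)/0.5981] = Φ(0.684) = 75%. Corrected power = Φ[(1.4937 − 1.2002)/0.5981] = Φ(0.491) = 69%. Required n is 85 per group, or 95 corrected.
- At 20%: pL = 0.121, pH = 0.279, d = 0.1575. Uncorrected power = Φ[(1.3636 − 1.1087)/0.5546] = Φ(0.460) = 68%. Corrected power = Φ[(1.2481 − 1.1087)/0.5546] = Φ(0.251) = 60%. Required n is 101 per group, or 113 corrected.

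**Step 4: other tests.** At the table's own ORs (2.9 at 20%, 2.8 at 25%), overall prevalence and 75 per group, two-sided power at 20% and 25% is:

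- pooled z: 70.4% and 75.3%
- unpooled z: 71.8% and 76.7%
- log-OR Wald: 67.8% and 73.1%
- arcsine: 71.7% and 76.1%
- exact chi-square: 71.6% and 75.8%
- Fisher: 64.0% and 69.9%
- continuity-corrected z: 62.8% and 68.8%

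None reaches 80%.

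**The case against.** The strongest reply is that this is a labelling ambiguity. The protocol never uses the word overall, and if 20% and 25% are meant as low-lipid rates the table is right to rounding. That stands in part: the arithmetic is sound under that reading. But neither the text nor the table says so, and both describe a prevalence in the patient population. On the low-lipid reading, the unmentioned consequence is that about a third of all patients would be FFR-positive. Either the label or the numbers must change.

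The second reply is that alpha is not stated. With a one-sided 0.05 uncorrected test and overall prevalence, power at 75 per group is 80.5% for OR 2.9 at 20% and 84.3% for OR 2.8 at 25%. So the shortfall does depend on assuming a two-sided test. The one-sided version gives 3.31, 2.62 and 2.29 for the 25% rows, however, against a printed 3.5, 2.8 and 2.4, so it is not how the table was made.

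Third, the lower power figures combine the change of reading with a conservative correction that the protocol does not name. This is fair, which is why both versions are shown. Uncorrected at 25%, the loss is modest: 75% power, and a detectable OR of 2.99 instead of 2.8.

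Fourth, FFR is a secondary endpoint, the primary being side-branch compromise, and no decision rule rests on OR 2.8. The risk of over-reading a null result is therefore a matter of interpretation. Even so, the 150 patients have no other stated justification.

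Finally, Procedures Involved in the Human Research limits side-branch FFR to patients whose post-stent angiogram shows stenosis below 70%, TIMI 3 flow and no dissection. Fewer than 75 per group may therefore contribute, and the recomputed figures are themselves upper limits on precision.

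**Conclusion.** The power statement is wrong as written. With 20% or 25% as the prevalence across two equal lipid groups, a two-sided 0.05 test, and FFR available in all 150 patients, 75 per group detects an OR of 3.3 or 3.0 uncorrected (3.7 or 3.2 corrected) with 80% power. Power for OR 2.8 is 60% to 75%, depending on the prevalence and the correction.

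That the table was built on the low-lipid rate is inferred from reproducing it; the protocol does not say so. The mismatch between label and numbers does not depend on what was intended. The two-sided alpha is an assumption, and a one-sided uncorrected test would largely close the gap without explaining the printed table.

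**What to change.** Choose one of two repairs, and in either case state the test, alpha and sidedness.

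1. **Keep the prevalence as a population figure and recompute.** For 50, 75 and 100 per group, uncorrected ORs are 4.6, 3.3 and 2.8 at 20%, and 3.9, 3.0 and 2.6 at 25%. Corrected ORs are 5.5, 3.7 and 3.0, and 4.5, 3.2 and 2.7. Change the conclusion for 75 per group to an OR of about 3.0 to 3.3 uncorrected, or 3.2 to 3.7 corrected.
2. **Keep the printed ORs and relabel.** Head the column as the FFR-positive rate in the low-lipid group, amend the text to match, and justify the overall prevalence of 31% to 37% implied at 75 per group. Give OR 2.9 at 20% and 2.8 at 25%.

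Under either repair, add that the figures assume an FFR value in every patient.

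The cost is an edit to one paragraph and one table. Enrolment stays at 150. The first repair makes the stated detectable OR less favourable; the second needs support for a higher overall prevalence.

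### The powered high- v low-lipid comparison is sized as a crude contrast, so it cannot show whether lipid predicts side-branch FFR ≤ 0.8 beyond calcium, which is already recorded

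*Combined protocol and SAP*

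**What the plan says.** All places are in the combined protocol and SAP.

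- **Sample size** (Data analysis and Statistical methods, under 5 Study Design). On the event rate: "We assumed FFR (+) prevalence of either 20% or 25% based on previous studies". On the split between groups, the text adds: "We also assumed that there would be a roughly equal proportion of patients with high and lipid levels"; the second group is evidently the low-lipid one. From these, "we will need at least 75 patients per EACH high lipid and low lipid groups to detect an odds ratio (OR) of 2.8". A six-row table then sets out "the detectable OR we might have under different assumptions of the patient population assuming an equal proportion of high/low lipid level groups"; its last column is headed "Detectable OR with 80% power".
- **Method** (same section). The only inferential method named is "T-test will be used". No regression model, covariate or stratification appears anywhere.
- **Population** (b Inclusion and Exclusion Criteria; f Procedures). The target lesion must be calcified, and patients are enrolled "who have moderate or severe calcification in the main vessel lesion identified by angiography". Both grades are defined there.
- **Calcium data** (f Procedures). OCT is done "to analyze plaque morphology, the extent and location of calcification, side branch size, angle, and ostial involvement".
- **Use of the calcium data** (e Study Endpoints). One secondary endpoint compares angiographic with OCT calcification. Another relates side-branch FFR to pre-PCI OCT measures in general. Neither puts calcium into the lipid comparison.
- **Timing** (f Procedures). Patients are randomised to rotational atherectomy or cutting balloon/PTCA. The pre-stent OCT pullback follows lesion preparation. FFR is measured only when the side branch has stenosis below 70%, TIMI 3 flow and no dissection.

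**The concern.** Lipid group is a property of the lesion, so randomisation does nothing to balance calcium between high- and low-lipid patients. Restricting entry to moderate or severe calcification narrows the range of calcium but does not fix it: two angiographic grades remain, and OCT extent varies within each. Lipid and calcium are components of the same plaque and may well be related. If calcium is also related to side-branch FFR, the crude lipid OR carries part of the calcium association.

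The study aims to find OCT predictors of functionally significant side-branch stenosis, in a population selected for calcium and treated by a calcium-directed randomisation. The first question about any lipid result will be whether it says more than the amount of calcium does. The analysis as written cannot answer that, although the data needed are collected.

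**Working it through.** **1. Reproduce the plan's figure.** Inputs: 25% FFR-positive, OR 2.8 and 80% power (all from the sample size text); two-sided alpha 0.05 (not stated, assumed). Take 25% as the low-lipid rate.

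- High-lipid rate: p2 = 0.25 × 2.8 / (1 - 0.25 + 0.25 × 2.8) = 0.70 / 1.45 = 0.483. Difference d = 0.233; mean rate 0.366.
- n = [1.960 √(2 × 0.366 × 0.634) + 0.842 √(0.25 × 0.75 + 0.483 × 0.517)]² / d² = (1.336 + 0.556)² / 0.0542 = 66.1, so 67 per group.
- With continuity correction: n/4 × [1 + √(1 + 4/(n d))]² = 16.52 × 4.505 = 74.4, so **75 per group**, as stated.

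The same formula gives detectable ORs of 3.72, 2.94, 2.55, 3.52, 2.79 and 2.43, against the table's 3.7, 2.9, 2.5, 3.5, 2.8 and 2.4. Reading 25% as the overall rate (0.157 v 0.343) needs 85 per group even without the correction. The table is therefore sound as a crude two-proportion calculation with 25% in the low-lipid group. It contains no allowance for a covariate.

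**2. The mechanism, by hand.** Assume severe calcium in 60% of low-lipid and 40% of high-lipid lesions, a calcium OR of 2 and a calcium-adjusted lipid OR of 2.8.

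- Low lipid: odds of 0.2136 in moderate lesions give risks of 0.176 (moderate) and 0.299 (severe). The group rate is 0.4 × 0.176 + 0.6 × 0.299 = 0.250.
- High lipid: odds of 0.598 and 1.196 give risks of 0.374 and 0.545. The group rate is 0.6 × 0.374 + 0.4 × 0.545 = 0.442.
- Crude OR = (0.442/0.558) / (0.250/0.750) = **2.4**, not 2.8. Simulated power is 70% crude and 82% adjusted.

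At a more extreme setting (70% v 30%, calcium OR 3) the crude OR is 1.7, with power 33% crude and 72% adjusted.

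**3. Continuous calcium, by simulation.** 150 patients; lipid and calcium bivariate normal; lipid split at the median; 25% FFR-positive in the low-lipid group; calcium OR 1.5 per SD; Wald tests with and without calcium.

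| Lipid-calcium correlation (assumed) | Crude OR when adjusted OR is 2.8 | Power, crude | Power, adjusted | Crude rejection, no lipid effect |
|---|---|---|---|---|
| -0.3 | about 2.2 | about 64% | about 80% | about 7% |
| -0.5 | about 2.0 | about 49% | about 76% | about 12% |

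With no calcium effect, this Wald test has about 85% to 87% power. That exceeds 80% because the table appears to include a continuity correction. The adjusted column uses the calcium measure itself; a two-level grade would recover only part of the gap.

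Direction and size depend on the assumptions. With 25% taken as the overall rate, a correlation of -0.1 moves 2.8 only to 2.56. If calcium is protective (OR 0.67 per SD, correlation -0.3 to -0.5), 2.8 is inflated to 3.29 to 3.75.

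**4. Cost of adjusting.** Approximate n becomes 75/(1 - R²), where R² is the share of lipid-group variance explained by calcium.

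- For two variables each split at the median, the correlation of the split variables is (2/π) arcsin(0.3 to 0.5) = 0.19 to 0.33, so R² is about 0.04 to 0.11.
- At R² 0.04: 75/0.96 = 78.1, so 79 per group, or a detectable OR of 2.85 if n stays at 75.
- At R² 0.10: 75/0.90 = 83.3, so 84 per group, or a detectable OR of 2.95.
- The unadjusted value is 2.79.

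**The case against.** The strongest reply is that the stated aim is prediction. A crude OR correctly describes how often FFR is positive in high- and low-lipid lesions, and the 2.8 in the sample size text is itself a detectable crude OR. If the crude association is 2.8, the planned power is unchanged. That stands. The power losses above arise only if 2.8 is the association at a given calcium level, which no section says. It is the reason to report both ORs.

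The other objections also carry weight:

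- Both associations are assumed, and the mildest null setting rejects at about 7%, close to nominal.
- OCT calcium is measured after randomised lesion preparation. Background says that atherectomy removes plaque, so this covariate may be altered by treatment.
- Other recorded features (baseline side-branch stenosis, size, angle, lipid location) could also matter. Calcium has the clearest claim because it defines the population, but it is not the only candidate.

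A reader might infer that the lipid result will be biased, or that the trial is underpowered because of calcium. The documents support neither inference, since they give no lipid-calcium or calcium-FFR figure. Nor is calcium wholly ignored: a secondary endpoint relates FFR to OCT measures in general.

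**Conclusion.** The point holds as a gap in the analysis plan. It is not an error in the sample size arithmetic. The only powered comparison is a crude contrast between non-randomised groups, and the plan does not use calcium data it already collects to ask whether lipid adds anything. That the analysis is unadjusted is inferred from the plan's silence and from the exact match to an unadjusted formula. A t-test on its own would not yield the OR that was powered.

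The size of any distortion cannot be derived. Under the stated assumptions, a conditional OR of 2.8 would appear as about 2.2 to 2.0, at a cost of roughly 16 to 27 power points (80 - 64; 76 - 49). With no lipid effect, the crude test would reject in about 7% to 12% of trials. Weaker associations give less distortion, and a protective calcium effect reverses its direction. The change is worth making because it is cheap and answers a question the result will certainly raise.

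**What to change.** For the lipid comparison, prespecify a logistic model of side-branch FFR ≤ 0.8 with three terms: lipid group, the angiographic moderate/severe calcium grade recorded at eligibility, and randomised arm. Report the adjusted lipid OR with the crude OR beside it. Repeat the model with OCT calcium extent as a sensitivity analysis, because that pullback follows lesion preparation. Define the lipid measure and its cut-off in the same paragraph; the plan gives no cut-off.

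Costs:

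- One or two extra degrees of freedom. At a 20% rate throughout, 0.20 × 150 = 30 events would support three terms at ten events each.
- A small power loss if calcium is unrelated to FFR: about 1 to 2 points at a correlation of -0.3, and more at stronger correlations.
- A detectable OR of about 2.85 to 2.95 at R² 0.04 to 0.10, which should be restated.
- Only partial adjustment, because the grade has two levels.
- Fewer than 150 patients, and fewer events, if any side branch has stenosis of 70% or more, TIMI below 3 or dissection, since FFR is then not measured. The restated detectable OR should allow for this.

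No new measurements or patients are required.
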